1.5 Rationale

We have performed an *in vitro* study of PAC-1 and entrectinib combination in seven uveal melanoma cell lines (GNAQ mutant: MEL270, 92.1, MEL202, OMM2.5, GNA11 mutant: OMM1, and GNAQ and GNA11 wild type: MEL285, and MEL290). In all seven cell lines we saw a synergistic killing effect of PAC-1 and entrectinib (data unpublished). We propose that entrectinib will synergize with PAC-1 in human patients with metastatic melanoma and will produce superior prolongation of PFS.

2 STUDY OBJECTIVES AND ENDPOINTS

2.1 Primary Objectives

2.1.1 Phase 1b

The primary objective of this study component is to determine the maximum tolerated dose (MTD) of PAC-1 in combination with entrectinib in patients with metastatic uveal melanoma, by evaluation of toxicity and tolerability.

2.1.2 Phase 2

The primary objective of this study component is to measure 3 months progression-free survival (PFS) rate in subjects with metastatic uveal melanoma treated with entrectinib and PAC-1.

2.2 Secondary Objectives

2.2.1 Phase 1b

Evaluate the safety of entrectinib and PAC-1 combination, assessed by the incidence and severity of drug-related adverse events (AE), in subjects with metastatic uveal melanoma.

2.2.2 Phase 2

- Evaluate the safety of entrectinib and PAC-1 combination, assessed by the incidence and severity of drug-related adverse events (AE), in subjects with metastatic uveal melanoma.
- Estimate the ORR in subjects with metastatic uveal melanoma treated with entrectinib and PAC-1.
- Estimate DoR in subjects with metastatic uveal melanoma.
- Estimate OS rate in subjects with metastatic uveal melanoma treated with entrectinib and PAC-1.

2.3 Correlative/Exploratory Objectives

- Determine pharmacokinetics (PK)/pharmacodynamics (PD) of PAC-1 alone after single dosing and after repeated dosing and in combination with entrectinib (Phase 1b only).
- Determine pharmacokinetics/pharmacodynamics of entrectinib alone after single dosing and after repeated dosing and in combination with PAC-1 (Phase 1b only).
- Compare procaspase 3 expression in tumor tissue to degree of clinical response
- Determine correlation between CTC number and clinical response.

2.4 Primary Endpoints

2.4.1 Phase 1b

- The MTD of PAC-1 in combination with entrectinib is the highest tested dose of PAC-1 combined with entrectinib with DLT rate of less than 33% in first cycle of therapy (i.e., ≤ 1 out of 6 subjects with DLT).

2.4.2 Phase 2

- PFS at 3 months; this is defined as proportion of alive subjects with metastatic uveal melanoma at 3 months from treatment initiation with PAC-1 in combination with entrectinib without evidence of radiological disease progression by RECIST 1.1.

2.5 Secondary Endpoints

2.5.1 Phase 1b

Safety and tolerability by NCI Common Terminology Criteria for Adverse Events (NCI CTCAE) Version 5 on treatment with PAC-1 in combination with entrectinib in subjects with metastatic uveal melanoma.

2.5.2 Phase 2

- Safety and tolerability by NCI Common Terminology Criteria for Adverse Events (NCI CTCAE) Version 5 on treatment with PAC-1 in combination with entrectinib in subjects with metastatic uveal melanoma.
- ORR; which will include CR + PR determined as per RECIST1.1 on treatment with PAC-1 in combination with entrectinib in subjects with metastatic uveal melanoma.
- DoR on treatment with PAC-1 in combination with entrectinib in subjects with metastatic uveal melanoma. DoR is defined as the time that measurement criteria are met for complete or partial response (whichever status is recorded first) until the date that

recurrent or progressive disease is objectively documented (taking as reference for progressive disease the smallest measurements recorded since treatment started).

- OS; this is defined as the time from treatment initiation with PAC-1 in combination with entrectinib until death as a result of any cause in subjects with metastatic uveal melanoma.

2.6 Correlative/Exploratory Endpoints

- PK endpoints of PAC-1 include plasma concentration-time curve from time 0 to 24 hours (AUC₀₋₂₄) for days 1 and 21 (see section on [Pharmacokinetic Analysis](#) for other endpoints) (Phase 1b only).
- PK endpoints of entrectinib include plasma concentration-time curve from time 0 to 24 hours (AUC₀₋₂₄) for days 3 and 21 (see section on [Pharmacokinetic Analysis](#) for other endpoints) (Phase 1b only).
- Compare procaspase 3 expression in tumor tissue to degree of clinical response.
- Determine correlation between CTC number and clinical response.

3 ELIGIBILITY REQUIREMENTS

3.1 Inclusion Criteria

Study entry is open to adults regardless of gender or ethnic background. While there will be every effort to seek out and include men and minorities, the subject population is expected to be no different than that of other advanced solid tumor cancer studies at each participating institution.

Subject must meet all of the following applicable inclusion criteria to participate in this study:

1. Written informed consent and HIPAA authorization for release of personal health information prior to registration. **NOTE:** HIPAA authorization may be included in the informed consent or obtained separately. Patients must be willing and able to provide written informed consent for this trial.
2. Age \geq 18 years at the time of consent.
3. Histologically or cytologically confirmed metastatic uveal melanoma. Staging per AJCC manual edition 8.
4. One or more lesions that could be accurately measured using Response Evaluation Criteria in Solid Tumors (RECIST) 1.1.
5. Eastern Cooperative Oncology Group (ECOG) performance status of 0 to 1 (Appendix 1).
6. Subjects must have archival tissue (metastatic disease preferred) available or undergo a biopsy prior to Cycle 1 Day 1 of treatment. Subjects that do not have archival tissue or cannot undergo a biopsy are not eligible for the study.

7. Demonstrate adequate organ function as defined in the table below. All screening labs to be obtained within 14 days prior to registration.

System	Laboratory Value
Hematological	
Leukocytes	$\geq 2,000 \mu/l$
Absolute Neutrophil Count (ANC)	$\geq 1,500 K/mm^3$
Platelets	$\geq 100,000/ mm^3$
Hemoglobin (Hgb)	$\geq 9 g/dL$
Renal	
Serum Creatinine	$\leq 1.5 \times ULN$
Calculated creatinine clearance ¹	$\geq 40 mL/min$
Hepatic	
Total Bilirubin	$\leq 1.5 \text{ mg/dL}$; (except for subjects with Gilbert Syndrome, who can have total bilirubin $<3.0 \text{ mg/dL}$)
Aspartate aminotransferase (AST)	$\leq 2.5 \times ULN$
Alanine aminotransferase (ALT)	$\leq 2.5 \times ULN$
Alkaline Phosphatase	$\leq 2.5 \times ULN$; ($<5 \times ULN$ if liver metastases present)
Coagulation	
Partial Thromboplastin Time (PTT)	$< 1.5 \times ULN$

¹ Cockcroft-Gault formula will be used to calculate creatinine clearance

8. Prior therapy is allowed but must have been completed 21 days prior to initiation of protocol therapy and all toxicities must be $<$ Grade 2.

9. Palliative radiation must have been completed 2 weeks prior to the initiation of study therapy.

10. Patient with known brain metastases must have been treated at least 2 weeks prior to enrollment, be asymptomatic from brain metastases, stable on brain imaging, and not be receiving a supra-physiologic dose of steroids ($>10 \text{ mg}$ prednisone daily or equivalent).

11. Women must not be pregnant or breastfeeding. All women of childbearing potential (WOCBP) must have a blood human chorionic gonadotrophin (hCG) test or urine hCG test within 2 weeks prior to registration to rule out pregnancy.

12. Women of childbearing potential (WOCBP) must agree to use contraception as outlined in Section 5.8 from the time of informed consent, during the study and for 3 months after the last dose of study drug(s). Abstinence from heterosexual intercourse is an acceptable form of contraception. Women of childbearing potential are those who have not been surgically sterilized or have not been free of menses >1 year.

13. Male patients who are sexually active with WOCBP must agree to use contraception as outlined in Section 5.8 from the time of initiation of study treatment, during the study and for 3 months after the last dose of study drug(s). Abstinence from heterosexual intercourse is an acceptable form of contraception.

14. The participant is capable of understanding and complying with the protocol and has signed informed consent document.

3.2 Exclusion Criteria

Subjects meeting any of the criteria below may not participate in the study:

1. Peripheral sensory neuropathy Grade ≥ 2 (per CTCAE v5.0).
2. Active gastrointestinal disease (e.g., Crohn's disease, ulcerative colitis, or short gut syndrome) or other malabsorption syndromes that would reasonably impact drug absorption.
3. Has known history of Human Immunodeficiency Virus (HIV) (HIV 1/2 antibodies).
4. Has known active Hepatitis B or C. Active Hepatitis B is defined as a known positive HBsAg result. Active Hepatitis C is defined by a known positive Hep C Ab result and known quantitative HCV RNA results greater than the lower limits of detection of the assay. For patients with past HBV infection or resolved HBV infection (defined as the presence of hepatitis B core antibody [HBcAb] and absence of HBsAg), the patient is only eligible if they are negative for HBV DNA.
5. Known interstitial lung disease, interstitial fibrosis, or history of tyrosine kinase inhibitor-induced pneumonitis. **NOTE:** Radiation-induced lung disorders are not included in this exclusion criterion.
6. History of retinal pigmented epithelial detachment, central serous retinopathy, or retinal vein occlusion in the unaffected eye; or intraocular pressure 21 mmHg or uncontrolled glaucoma (irrespective of intraocular pressure) in the unaffected eye.
7. History of uncontrolled seizures.
8. History of ataxia.
9. Allergies and adverse drug reaction: History of allergy to study drug components.
10. Thromboembolic events requiring therapeutic anticoagulation. Concomitant anticoagulation with oral anticoagulants (warfarin, direct thrombin or factor Xa inhibitors), platelet inhibitors (e.g. Clopidogrel, high dose aspirin) is prohibited. Low-dose aspirin (≤ 100 mg/day), low-dose warfarin (≤ 1 mg/day) and prophylactic low molecular weight heparin (LMWH) or similar agent are permitted.
11. History of recent (within the past 3 months) symptomatic congestive heart failure or ejection fraction $\leq 50\%$ observed during screening for the study.
12. History of prolonged QTc interval (e.g., repeated demonstration of a QTc interval > 450 milliseconds from ECGs performed at least 24 hours apart).

13. History of additional risk factors for torsades de pointes (e.g., family history of long QT syndrome).
14. Cardiovascular disorders including unstable angina pectoris, clinically-significant cardiac arrhythmias, myocardial infarction or stroke (including transient ischemic attack [TIA], or other ischemic event) within 6 months prior to registration.
15. Active infection requiring intravenous systemic treatment.
16. Serious non-healing wound/ulcer/bone fracture within 28 days prior to registration.
17. Known uncontrolled, symptomatic brain metastasis or cranial epidural disease.
18. Known additional malignancies which require systemic treatment.
19. Inability to swallow intact tablets.
20. Other severe acute or chronic medical or psychiatric condition or laboratory abnormality that may increase the risk associated with study participation or study drug administration or may interfere with the interpretation of study results and, in the judgment of the Investigator, would make the patient inappropriate for entry into this study or could compromise protocol objectives in the opinion of the Investigator and/or the sponsor-investigator.

4 SUBJECT REGISTRATION

All subjects must be registered through HCRN's electronic data capture (EDC) system. A subject is considered registered when an "On Study" date is entered into the EDC system. Subjects must be registered prior to starting protocol therapy. Subjects must begin therapy **within 7 business days** of registration.

5 OVERALL DESIGN AND TREATMENT PLAN

5.1 Phase 1b Dose Escalation Plan

This Phase Ib dose escalation study will evaluate entrectinib in combination with PAC-1 in subjects with metastatic uveal melanoma. Entrectinib will be taken orally on Days 1-28 of each 28 day cycle and PAC-1 will be taken orally on Days 1-21 of each 28-day cycle (see exception for Cycle 1 below), and response to treatment will be evaluated after every 2 cycles. Treatment will continue until disease progression (based on RECIST 1.1 criteria), unacceptable toxicity, subject withdrawal of informed consent, or subject death either from progression of disease, the therapy itself, or from other causes. Subjects who withdrew from study treatment, have progressive disease, or unacceptable toxicities will be followed for survival every 2 months for 12 months from start of study treatment, then every 3 months for up to 24 months.

Pharmacokinetic (PK) and pharmacodynamic (PD) assay for PAC-1 will be performed during Days 1 and 21 of Cycle 1. PAC-1 will be given on Day 1 of Cycle 1, withheld on Day 2 and Day 3 of Cycle 1 then reinitiated on Day 4 of Cycle 1 to continue to Day 21 of the 28-day cycle. For

each successive cycle, PAC-1 therapy will be initiated on Day 1 and continue to Day 21 of the 28-day cycle.

Pharmacokinetic and pharmacodynamic assay for entrectinib will be performed during Days 3 and 21 of Cycle 1. Entrectinib therapy will be withheld on Day 1 and Day 2 of Cycle 1, initiated on Day 3 of Cycle 1 and continue for the remainder of the cycle. For each successive cycle, entrectinib will be initiated on Day 1 and continue for the remainder of the 28 day cycle.

Cycle 1 of Treatment (Cycle = 28 Days)

Drug	Dose	Route	Cycle 1 Frequency
PAC-1	TBD	Orally	Day 1 then Day 4 to Day 21; HELD Day 2 and Day 3
Entrectinib	600 mg		Day 3 to Day 28; HELD Day 1 and Day 2

Cycle 2 and Subsequent (Cycle = 28 Days)

Drug	Dose	Route	Frequency
PAC-1	TBD	Orally	Day 1 to Day 21
Entrectinib	600 mg		Day 1 to Day 28

Study Treatment Dose Levels

Dose Level*	PAC-1 Dose (mg, orally)	Entrectinib (mg, orally)	# of Subjects [^]
-1	625 daily	400 daily	3-6
1 (starting)	625 daily	600 daily	3-6
2	750 daily	600 daily	3-6

*Pharmacokinetics analysis will be performed at both dose levels during Cycle 1.

[^]MTD cohort will be initially expanded to 6 patients, and if no DLT move to Phase 2 study.

5.1.1 Dose Escalation Rules and MTD Definition

- Three subjects will initially be enrolled at dose level 1. If none of the 3 subjects experience a dose limiting toxicity (DLT) during the first cycle of therapy, three subjects will be enrolled at dose level 2. If all subjects in dose level 2 complete the first cycle of therapy without DLT, 3 more subjects will be enrolled into dose level 2 to ensure only 0-1 of 6 subjects have a DLT. There will be no further escalation beyond dose level 2.
- Alternatively, if 1 of the first 3 subjects within a dose level cohort experiences a DLT, the cohort will be expanded to 6 subjects. If this happens within dose level 1 and only 1 of the total 6 subjects in dose level 1 experience DLT, the study will proceed to dose level 2. If 2 or more of 6 subjects in a cohort experience DLTs, or 2 subjects within a cohort of 3 subjects experience DLT during the first cycle of therapy (>33% of subjects experiencing DLT), the MTD is exceeded. If this occurs at dose level 1, additional subjects will be accrued to dose level -1. If this occurs at dose level 2, 3 additional subjects will be

enrolled into dose level 1, unless there have been 6 subjects already enrolled into dose level 1.

- The MTD of PAC-1 in combination with entrectinib is the highest tested dose of PAC-1 combined with entrectinib with DLT rate of less than 33% in the first cycle of therapy (i.e., ≤ 1 out of 6 subjects with DLT). That dose will be recommended for the Phase 2 study.
- At the discretion of the sponsor-investigator, a lower Phase 2 dose may be recommended if other toxicity emerges during the Phase 1b study which does not meet DLT criteria but limits the dose that can be administered cumulatively.

5.1.2 Definition of Dose-Limiting Toxicity

Toxicity and adverse events will be classified according to NCI's Common Terminology Criteria for Adverse Events Version 5.0 (CTCAE v.5).

Dose limiting toxicity (DLT) is defined as one of the following events **that are at least possibly related** to study medications occurring during Cycle 1 (first 28 days):

- Grade 3 or greater hematologic toxicity during the first cycle (28 days) of therapy.
- Cerebrovascular ischemia or cerebrovascular hemorrhage of any duration or grade.
- Grade 3 or greater clinical non-hematological toxicity (excluding \geq grade 3 nausea, vomiting, or diarrhea lasting less than < 72 hours with maximal medical intervention and/or prophylaxis) during the first cycle (28 days) of therapy.
- Delay of Cycle 2 treatment start by more than 2 weeks due to incomplete hematologic recovery ($ANC \geq 1.5 \times 10^9/L$ or platelets $\geq 100 \times 10^9/L$) or unresolved treatment related grade 3 or greater non-hematologic toxicity.
- Grade 2 or greater treatment related neurological toxicity occurring during the first cycle of therapy and lasting more than 72 hours.
- Hepatic labs meeting Hy's Law (concomitant elevations of AST/ALT and bilirubin of 3x ULN and 2xULN respectively without alternative etiology)

DLT's will be counted based on the number of patients with DLT at a given dose level, not the absolute number of DLTs. No single patient can trigger more than one DLT event. Additional patient cohorts will not be enrolled until all patients at the current dose level complete all planned treatment for Cycle 1 and are able to start Cycle 2 with no more than a 2-week delay.

Intra-subject dose escalation is not permitted. Once the MTD of PAC-1 in combination with entrectinib is determined, enrollment will continue until at least 6 subjects total are accrued at the maximum tolerated dose.

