6.1 Start of a New Cycle

A new treatment cycle will only be initiated when all of the following conditions are met:

- ANC $\geq 1,500/\text{mm}^3$
- platelets $\geq 100,000/\text{mm}^3$
- non-hematologic treatment related toxicities have improved to \leq Grade 1 or to the patient's baseline values (except alopecia)

If blood counts are below this threshold, blood work is to be repeated weekly until counts are at an acceptable level. Treatment will be restarted with appropriate dose modifications. If treatment is unable to restart within 4 weeks of the planned treatment date, the patient will be permanently discontinued from study therapy. **NOTE:** For Cycle 1 of the Phase 1b study only, the inability to restart therapy within 2 weeks of the planned date is a DLT (per section 5.1.2); however the patient is allowed an additional week of recovery and is allowed to remain on study if treatment restarts within 4 weeks.

For subjects who present to the clinic with toxicity during a current treatment cycle, the study drug may be stopped per the discretion of the site investigator if the toxicity is determined to be clinically significant.

Dosing interruptions are permitted in the case of medical / surgical events or logistical reasons not related to study therapy (e.g., elective surgery, unrelated medical events, patient subject vacation, and/or holidays). Subjects should be placed back on study therapy within 4 weeks of the scheduled interruption, unless otherwise discussed with the sponsor-investigator. The reason for interruption should be documented in the patient's subject's study record.

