6.2 Dose Modifications for PAC-1 Toxicity

CTCAE v 5 Adverse Effects Terms & Descriptions)	PAC-1 Dose Modifications
Any other grade 3 non-hematologic toxicity	Hold dose until improvement to grade ≤ 1 then decrease dose by one dose level below level that caused toxicity.
Grade ≥ 2 neurologic toxicity detected at any time while on study treatment	Hold dose until improvement to grade ≤ 1 then decrease dose by one dose level below level that caused toxicity.
Any grade cerebrovascular ischemia or hemorrhage	Discontinue treatment.
Any other grade 4 non-hematologic toxicity	Discontinue treatment.
Neutrophils < 500 cells/mm 3	Hold dose until improvement to grade ≤ 1 then decrease dose by one dose level below level that caused toxicity.
Febrile Neutropenia	Hold dose until improvement to grade ≤ 1 then decrease dose by one dose level below level that caused toxicity.
Platelets $< 25,000/\text{mm}^3$ or platelets $< 50,000/\text{mm}^3$ with bleeding	Hold dose until improvement to grade ≤ 1 then decrease dose by one dose level below level that caused toxicity.
Any other grade 3 hematologic toxicity	Hold dose until improvement to grade ≤ 1 then decrease dose by one dose level below level that caused toxicity.
Any other grade 4 hematologic toxicity	Discontinue treatment.

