Congestive heart failure	Continue at same dose level	Withhold dose until toxicity is \leq G1 or has returned to baseline, then reduce by 1 dose level and resume treatment	Withhold dose until toxicity is \leq G1 or has returned to baseline, then reduce by 1 dose level and resume treatment	Discontinue treatment permanently

Pneumonitis (in absence of disease progression, pulmonary embolism, positive cultures or radiation effect)	Withhold dose until toxicity is Grade 0, then resume treatment at same dose Discontinue treatment permanently if pneumonitis recurs	Withhold dose until toxicity is Grade 0, then resume treatment at same dose Discontinue treatment permanently if pneumonitis recurs	Discontinue treatment permanently	Discontinue treatment permanently
Hyperuricemia symptomatic or Grade 4	
Initiate urate-lowering medication.
 
 Withhold entrectinib until improvement of signs or symptoms. Resume entrectinib at same or reduced dose. 			
Hepatotoxicity	Continue at same dose level	Continue at same dose level	
Withhold dose until recovery to \leq Grade 1 or to baseline.
 
Resume at same dose if resolution occurs within 4 weeks.
 
Permanently discontinue if adverse reaction does not resolve within 4 weeks.
 
Resume at a reduced dose for recurrent Grade 3 events that resolve within 4 weeks.
	
Withhold dose until recovery to \leq Grade 1 or to baseline.
 
Resume at same dose if resolution occurs within 4 weeks.
 
Permanently discontinue if adverse reaction does not resolve within 4 weeks.
 
Permanently discontinue for recurrent Grade 4 events

	ALT or AST greater than 3 times ULN with concurrent total bilirubin greater than 1.5 times ULN (in the absence of cholestasis or hemolysis) permanently discontinue treatment.			
Other Clinically Relevant Adverse Reactions	Grade 3 or 4		
Withhold entrectinib until adverse reaction resolves or improves to recovery or improvement to Grade 1 or baseline.
 
Resume at the same or reduced dose, if resolution occurs within 4 weeks.
 
Permanently discontinue if adverse reaction does not resolve within 4 weeks.
 
Permanently discontinue for recurrent Grade 4 events.
	

*dose modifications to be based on worst toxicity grade as per NCI CTCAE v5.0

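### The DLT list in Section 5.1.2 does not count some Cycle 1 toxicities that stop a study drug, and its delay and cohort-opening rules do not fit Sections 6.1 and 5.1.1

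*Combined protocol and SAP*

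**What the plan says.** All references are to the combined protocol and SAP.

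- **Section 5.1.2, closed list.** "Dose limiting toxicity (DLT) is defined as one of the following events", followed by six bullets. Events must be at least possibly related and fall in Cycle 1. No bullet refers to stopping a drug.
- **Section 5.1.2, hepatic bullet.** "concomitant elevations of AST/ALT and bilirubin of 3x ULN and 2xULN respectively without alternative etiology".
- **Section 5.1.2, third bullet.** Clinical non-hematologic toxicity of Grade 3 or more counts. The exception is at least "grade 3 nausea, vomiting, or diarrhea lasting less than < 72 hours with maximal medical intervention and/or prophylaxis", with no upper grade on the exception.
- **Section 5.1.2, delay bullet.** A Cycle 2 delay of more than 2 weeks counts if it is due to incomplete hematologic recovery or "unresolved treatment related grade 3 or greater non-hematologic toxicity".
- **Section 5.1.2, cohort opening.** No further cohort may enroll until every patient at the current level has finished all planned Cycle 1 treatment and can start Cycle 2 no more than 2 weeks late.
- **Section 6.2.** For "Any other grade 4 non-hematologic toxicity" the action is to discontinue treatment.
- **Section 6.3.** Entrectinib is stopped permanently for "ALT or AST greater than 3 times ULN with concurrent total bilirubin greater than 1.5 times ULN", absent cholestasis or hemolysis. It is also stopped permanently when Grade 1 or 2 pneumonitis recurs.
- **Section 6.1.** A new cycle starts only when "non-hematologic treatment related toxicities have improved to" Grade 1 or lower, or to baseline. A note for Cycle 1 of Phase 1b adds that "the inability to restart therapy within 2 weeks of the planned date is a DLT (per section 5.1.2").
- **Section 5.1.1.** The MTD is the highest tested dose with at most 1 of 6 subjects having a DLT.

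**The concern.** The Phase 1b primary endpoint is a count of DLTs in at most six subjects per level, so one subject's classification can decide it. If the protocol takes a subject off one of the two drugs for related toxicity in Cycle 1, that subject has not tolerated the combination. Yet under some entries in the dose-modification tables the same subject is a non-DLT in the count that sets the MTD. The accepted dose then goes to 29 further subjects (Section 12.3.1).

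Two wording conflicts add to this. The delay rule gives different answers in Sections 5.1.2 and 6.1, so two sites could classify the same subject differently. The cohort-opening sentence, read literally, cannot be met once any subject fails to complete Cycle 1, although Section 5.1.1 allows escalation from level 1 with 1 DLT in 6.

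**Working it through.** **Step 1: compare the stop entries in 6.2 and 6.3 with the six DLT bullets.** Most are covered: cerebrovascular events, Grade 4 hematologic toxicity, Grade 4 CNS effects, Grade 4 heart failure and Grade 3-4 pneumonitis. Three are not. The trigger for one permanent stop under QT prolongation could not be read in the copy available, so it is not classified here.

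| Related Cycle 1 event | Dose-modification table | DLT under 5.1.2? |
|---|---|---|
| ALT/AST >3x ULN, bilirubin >1.5x but <2x ULN | 6.3: entrectinib stopped permanently | No; the hepatic bullet needs 2x ULN |
| Grade 4 vomiting or diarrhea, under 72 h with maximal intervention | 6.2: PAC-1 discontinued | No; excluded from the third bullet |
| Recurrent Grade 1-2 pneumonitis | 6.3: entrectinib stopped permanently | No bullet applies |

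The hepatic row assumes that both values grade below 3, or that laboratory values fall outside the third bullet's restriction to clinical toxicity. The documents do not print the CTCAE cut-offs. There is some internal support: the hepatotoxicity row in 6.3 continues dosing at Grades 1 and 2 and states the combined ALT/bilirubin rule separately. The pneumonitis row needs onset, full resolution, restart and recurrence within 28 days, so it will be rare.

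**Step 2: compare the delay rules.** Take a related Grade 2 non-neurological toxicity that persists for 3 weeks past the planned Cycle 2 start. Section 6.1 blocks Cycle 2 because the toxicity is above Grade 1 (and, by assumption, above baseline), and its note makes the delay a DLT. The 5.1.2 delay bullet does not, because the toxicity is below Grade 3. Neurological Grade 2 toxicity lasting more than 72 hours has its own DLT bullet, so the conflict is confined to other toxicities.

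**Step 3: compare cohort opening with 5.1.1.** Suppose 1 of 6 subjects at level 1 has a DLT and stops treatment during Cycle 1. Section 5.1.1 proceeds to level 2. The 5.1.2 sentence requires all patients to have completed planned Cycle 1 treatment, and this subject never will.

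**Step 4: effect on the level 2 verdict.** Inputs: the 5.1.1 rule (1/6 = 16.7%, accepted; 2/6 = 33.3%, exceeded), one subject with an uncounted stop, and all 2^5 = 32 DLT patterns in the other five.

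| Other counted DLTs | Patterns | As written | If the stop is counted |
|---|---|---|---|
| 0 | 1 | 0/6, MTD | 1/6, MTD |
| 1 | 5 | 1/6, MTD | 2/6 (or 2/3), exceeded |
| 2 or more | 26 | exceeded | exceeded |

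The verdict changes only with exactly one other counted DLT.

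**Step 5: illustration with assumed rates.** The documents give none. Let q be the probability that a subject has a counted event. Level 2 is accepted with probability (1-q)^6 + 6q(1-q)^5. Assume listed DLTs occur in 20% of subjects, and uncounted stops in a further 1%, 5% or 15%, in different subjects.

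- As written, q = 0.20: 0.262 + 0.393 = 0.655
- Counting a further 1%, q = 0.21: 0.243 + 0.388 = 0.631
- Counting a further 5%, q = 0.25: 0.178 + 0.356 = 0.534
- Counting a further 15%, q = 0.35: 0.075 + 0.244 = 0.319

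The low end is the more plausible. The hepatic window is narrow, and Day 15 is the only scheduled chemistry panel between Cycle 1 Day 1 and Cycle 2 Day 1 (Section 7, footnote 5).

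**The case against.** DLT criteria and dose-modification rules need not coincide. A cautious stopping threshold for the individual can sit beside a more specific DLT threshold. The 2x bilirubin cut is the Hy's Law criterion and recurs in Section 11.1.3.3, so it looks deliberate. The 72-hour exclusion is also explicit. This stands as a reason to leave the thresholds alone. It does not explain why a subject who has to come off a drug should enter the MTD count as a non-DLT.

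The 6.1 note cites 5.1.2, so it might be read as importing that section's conditions, and it sits in a paragraph that opens with blood counts. That reading is possible, but the note's wording is limited neither to hematologic causes nor to Grade 3.

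Safeguards exist. Section 5.1.1 lets the sponsor-investigator recommend a lower Phase 2 dose for toxicity short of a DLT. Section 5.2 has DSMB recommendations reviewed before Phase 2. Section 11.2.5 makes every Grade 4 event a reportable SAE. These soften the consequence, but none changes the DLT count.

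A reader might infer that an uncounted stop among the first three subjects at level 1 would lead straight to escalation at 0/3. The documents do not support that. If the stop leaves planned Cycle 1 doses untaken, the completion rule in 5.1.2 literally blocks a new cohort. A similar limit applies within level 2, where 5.1.1 asks the first three subjects to complete Cycle 1 without DLT before three more enroll. The change of verdict is therefore clearest for a stop among subjects 4-6, or in the first three alongside the counted DLT that triggers expansion.

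**Conclusion.** The point holds as a cheap improvement. The text establishes three things: table-mandated stops that are not DLTs, a delay rule that differs between 5.1.2 and 6.1, and a cohort-opening sentence that conflicts with 5.1.1. The brief Grade 4 vomiting or diarrhea case and the delay conflict need no outside cut-offs. The hepatic case rests on the grading assumption in Step 1.

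The size is unknown and probably small. The clear consequence is at level 2: one uncounted subject with exactly one counted DLT gives 1/6 and an accepted MTD, where counting both gives 2/6 and a dose that exceeds it.

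Two stronger readings should be resisted. Section 6.2 says to discontinue but, unlike 6.3, does not say permanently, so only the entrectinib stops can be called permanent. And without event rates, nothing shows that an intolerable dose is likely to be selected.

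**What to change.** Leave the bilirubin cuts in 5.1.2, 6.3 and 11.1.3.3 unchanged, and make three edits.

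(a) Add a bullet to 5.1.2: *any at least possibly related Cycle 1 toxicity, without alternative etiology, for which the tables in Section 6.2 or 6.3 require discontinuation of PAC-1 or entrectinib, other than stops triggered by failure to recover within a set time.* Delay-based stops are left out because 6.2.1 and 6.3.2 use 2 weeks while 6.1 and 6.4 use 4. If the sponsor considers brief Grade 4 vomiting or diarrhea tolerable, exempt it from the 6.2 stop instead.

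(b) Make the 5.1.2 delay bullet and the 6.1 note agree. Preferably, count a Cycle 2 delay of more than 2 weeks from any treatment-related toxicity that fails the 6.1 restart criteria. This is a substantive change: it lowers the non-hematologic delay threshold from Grade 3 to Grade 2. The alternative is to limit the 6.1 note to the causes listed in 5.1.2, which removes the conflict without widening the DLT definition.

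(c) In the cohort-opening sentence, add *or have been counted as a DLT*.

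The cost is one bullet and two wording edits, with no change to visits or sample size. The downside is an occasional extra DLT: in subjects with raised baseline liver values (limited by the alternative-etiology wording), in rare recurrent low-grade pneumonitis, and, under the preferred form of (b), in subjects with a persistent Grade 2 toxicity.
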